 - Save the Session data to the USB drive.

- Perform Inspection and Maintenance on hearing aids and enter findings in REDCap
 - **DO NOT do this where the participant can see what is being done, as this could influence PHAST-R results.**
 - Do a listening check on hearing aids to determine Program being used.
 - Put hearing aids in a charger to check battery levels. If not charged, charge until sufficient for testing. Take out of charger.
 - Clean or replace any domes or wax filters if blocked with cerumen.
 - Replace any damaged receiver wires
 - **DO NOT provide any instruction/re-instruction to participant regarding use/care of hearing aids at this point in the session. A structured protocol to address this will be available later in the session.**
 - Set aids to Program 1 and complete on-ear speech mapping for each ear:
 - Select **Test 1:** ISTS/ Avg (65)
 - Select **Test 2:** ISTS/ Soft (55).
 - Select **Test 3:** ISTS/Loud (75)
 - MPO/LDL measurement: use instructions and categories on printed sheet. [Link to MPO LDL document](#)

Instructions:

“The purpose of this test is to determine if your hearing aids are set so that sounds get what you feel is ‘Uncomfortably Loud’. Here are categories of sound that describe loudness, from ‘Very Soft’ up to ‘Uncomfortably Loud’. We know that sometimes sounds are ‘Loud but OK’ but we do not want them to be ‘Uncomfortably Loud.’ I am going to play out a sound that will be changing in pitch. Raise your hand or tell me to stop the sound if you feel that it is “Uncomfortably Loud”. If it is “Loud, but OK”, then do not tell me to stop.”

Categories of Loudness:

- Uncomfortably loud
- Loud, but okay
- Comfortable, but slightly loud
- Comfortable
- Comfortable, but slightly soft

- Soft
- Very soft
- Select **Test 4** = MPO/85 dB SPL
- Note in REDCap if participant indicated that the signal was “Uncomfortably loud”
- Do NOT return hearing aids to participant until PHAST-R testing

Aided Questionnaires

- Hand iPad to participant and instruct them to *answer questions till they arrive at a screen that asks them to hand the iPad back to the audiologist.*

The participant will complete these questionnaires on REDCap without assistance:

- Aided [PHAP](#)
- Aided [HHIE](#)
- [MARS-HA](#)
- For AB Group, skip to [Save Verifit Data](#)
- For CD and EF Groups, do NOT save Session data #2 until after test box measures are completed.

For CD and EF Groups Only

Obtain test-box measures

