13.5.3 Check Hearing Aid Problems Inventory [AudU]

Ask the participant, “**Have you been having any problems with your hearing aids? [If Yes] What are they?**”

- Complete the inventory on REDCap to mark each problem that the participant reports.
- Mark the appropriate sections on a hard copy of the Trouble Shooting Guide.
- Ask if participant still has the user’s manual. Provide new copy if they do not.

Problems charging the hearing aids? R__ L__ p.13-15

Problems putting the aids in your ears? R__ L__ p.18

Problems removing the aids? R__ L__ p.18

Problems with the hearing aids whistling or buzzing? R__ L__ p.18

Problems changing the program in the aids? p.21

Hearing aids are not loud enough? p.21

Hearing aids sound too loud? p.21

Hearing aids sound too tinny? p.21

Hearing aids sound distorted? p.13-15

Problems changing the domes? p.29

Problems changing the wax guards? p.33

Problems keeping aids in ears? Audiologist can install Sport Lock on aids if needed

Ask the participant, “Are you going to keep your hearing aids?”

If “Yes”, keeping hearing aids:

- Continue to [13.5.4 Payment for Session 2](#)

If “No”, not keeping hearing aids:

- Read Instructions and Participant Debriefing Script in REDCap.
- Complete repeat audiogram and enter results in REDCap following instructions
- Complete Exit form in REDCap following instructions
- Continue to [13.5.4 Payment for Session 2](#)
- Follow instructions for Refunding Payment in next section.

After participant leaves, continue to [Session 2 Wrap-Up](#)

13.5.4 Payment for Session 2

After Session 2, AudU will provide the \$20 travel reimbursement gift card remind participant that they will be contacted to have Session 3 scheduled

To process gift card:

- Complete receipt on REDCap
 - Participants will be asked if they are a Northwestern Employee.
 - If participant selects “yes” a new set of fields will become available and should be completed.
 - If the participant is a temporary employee, print the linked DCFS form and obtain the participant’s signature.
 - Upload a photo of the DCFS form on REDCap
- Complete payment process on Clover device (for more, see [Clover Tips document](#))
 - Enter your Clover device password.
 - Tap **Register**
 - Scan \$20 travel reimbursement gift card.
 - Tap **Review Order**. Make sure gift card “costs” \$0.00.
 - Tap **Pay**
 - Select **Check**

- In **Note**, please add Participant ID
- Select **Print Receipt**
- Hand gift card and receipt to participant.

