REMIND PARTICIPANT: PLEASE REMEMBER TO USE YOUR HEARING AIDS FOR AT LEAST FOUR HOURS EACH DAY.

- **Refunding Payment:** If participant is returning the hearing aids, a refund needs to be processed for the \$650 on the Clover device. For more details, see [Clover Tips document](#).
 - Enter your Clover device password.
 - Open the Refund app.
 - REDCap will display the date of Session 1 that order was placed
 - If Session 1 was less than 30 days prior, select “Look Up Past Payment” and transactions will be displayed by date from most recent; scroll to find date.
 - Tap transaction and confirm name and last digits of card number are correct by selecting “Details”.
 - Select REFUND button.
 - If Session 1 was more than 30 days prior (which most will be), the transaction will not appear; Enter amount to refund manually:
 - \$635.70 + \$14.30 tax = \$650.00 total
 - Select Issue Refund
 - Enter credit or debit card number, expiration date, and CVV
 - If a check was used for payment, select Cash refund and notify P-CHAT office that a refund check needs to be sent to participant. Tell participant that they will receive a check from NU within a few weeks.
 - Print and provide receipt for refund to participant.
 - Take the box of aids with charger from participant to be returned.

When participant leaves, continue to [Session 2 Wrap-Up](#)

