15.0 Exit Protocol

At each stage of the study, there are points at which the participant may choose to exit the study. If appropriate, research team members can encourage participants to remain in the study. The following outlines the various points where exit from the study may occur. When this happens, [the Exit form and Gift Card Receipt form](#) in REDCap need to be completed.

- Session 1 screening
 - Does not qualify
 - Complete exit form (select exit at “Screening”)
 - Qualifies but decides not to continue
 - Complete exit form (select exit at “Session 1”)
- Session 1 data
 1. Decides not to continue with hearing aids *before* fitting
 - i. Complete exit form. Include details about exit reason(s).
 2. Decides not to continue with hearing aids *after* fitting
 - i. Encourage to try hearing aids till Session 2
 - ii. Remind that they can get a complete refund at Session 2
 - iii. Complete exit questionnaire if participant still wants to withdraw
- Session 1 no show
 3. Coordinating center calls and attempts to rescheduleIf unreachable or unwilling to reschedule
Complete exit questionnaire on the phone
- Calls to cancel Session 2 appointment
 4. Encourage to keep Session 2 appointmentProvide hearing aid return instructions to Coordinating Center
Inform that \$650 will be returned once hearing aids are received
Complete exit questionnaire if participant still wants to withdraw
- Session 2
 5. Hearing aid returnedAudiogram
Fill out exit questionnaire if participant still wants to withdraw
 6. Hearing aid not returned but will not return for session 3Encourage to keep session 3 appointment
Remind about \$75 completion gift card
Audiogram
Fill out exit questionnaire if participant still wants to withdraw
- Session 2 No Show
 7. Coordinating center calls and attempts to rescheduleIf unreachable or unwilling to reschedule
Complete exit questionnaire on the phone

- Calls to cancel Session 3 appointment
 8. Encourage to keep session 3 appointment
 - Remind about \$75 completion gift card
 - Fill out exit questionnaire if participant still wants to withdraw
- Session 3 Completes study
 - Audiogram
 - Fill out exit questionnaire
- Session 3 No show
 9. Coordinating center calls and attempts to reschedule
 - If unreachable or unwilling to reschedule
 - Complete exit questionnaire on the phone

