Based on prior work of a similar nature ([name] et al., 2019; [name] et al., 2017), it was assumed that about 36% of those who enrolled would have audiometrically defined normal hearing (better-ear PTA4 < 20 dB HL), better than the sponsor-required range of mild to moderate audiometric hearing loss. As a result, a total of 389 individuals (130 per group) were targeted for study completion (Session 3) so that at least 249 individuals (83 per group) with mild or moderate hearing loss would be included in the analyses. Assuming, again based on experience with similar RCTs, that overall attrition from study enrollment to the 6-month follow-up would be about 35%, the target enrollment at Session 1 was established to be 591 (197 per group).

A total of 584 adults enrolled at Session 1, but both the percentage with normal hearing and the attrition rates were lower than anticipated. In the end, enrollment of 584 participants in Session 1 resulted in 172, 171 and 180 adults with mild or moderate audiometric hearing loss assigned to the AB, CD, and EF groups. Of these, 152, 133, and 138 completed all three sessions for groups AB, CD, and EF, respectively. Based on the desired sample size of 64 per group for the primary (PHAB global) and secondary (HHIE total benefit) outcome measures, as well as the sample size of 83 per group targeted for eventual APHAB global analyses, the intention-to-treat (ITT) and per-protocol (PP) analyses were sufficiently powered. In addition, when the numbers of those with mild or moderate audiometric hearing loss in each group were tabulated, ITT analyses were sufficiently powered (group sizes > 64) to perform sensitivity analyses for each hearing-loss severity separately using the primary and secondary outcome measures.

As noted, in addition to the PHAB-global and HHIE-total benefit primary and secondary outcome measures, a measure of quality of life, the PROMIS-10 Global (Hays et al., 2009), was obtained at Sessions 1 and 3. In particular, the raw PROMIS physical-health and mental-health scores were computed following PROMIS-10 guidelines, and these two subscale scores represented an additional long-term outcome measure obtained in this RCT. No non-inferiority

4

margin was established *apriori* for this measure because it was not the primary or secondary outcome and because few data were available from RCTs of hearing-aid interventions that had used the PROMIS-10 Global.

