**Analyses:** Some participants in each branch decided to withdraw from the study prior to completion. All participants remained in the branch to which they were randomly assigned at study outset. SAS Version 9.4 was used to impute missing data using the Markov Chain Monte Carlo (MCMC) method (n=20 imputations) and the multivariate-normal approach. Both ITT and PP analyses were performed, as has been recommended (Rehal et al., 2016). After addressing the missing data, initial analysis of the effects of fitting method followed the recommendations by the International Conference on Harmonization (2001; 1998) and CONSORT (Piaggio et al., 2001; Piaggio et al., 2006). The primary focus of the analyses is the comparative effectiveness of each self-fitting method (CD, EF) to best practices (AB). Finally, sensitivity analyses were performed by examining the outcomes separately for those with mild versus moderate audiometric hearing loss. All statistical analyses used SPSS Version 29.0.1.0. This included boot-strapped (n=1000; Biascorrected and accelerated, BCa) General Linear Model analyses, t-tests, means, and 95% confidence intervals.

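### The ITT analysis imputes as if data were missing at random although non-completion in CD and EF is about twice that in AB, and no listed sensitivity analysis tests that assumption

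*SAP*

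**What the plan says.** The Analyses paragraph of the SAP says that SAS was used to "impute missing data using the Markov Chain Monte Carlo (MCMC) method (n=20 imputations) and the multivariate-normal approach" and that both ITT and per-protocol analyses were run. It does not name the missing-data assumption, list the variables in the imputation model or define the per-protocol set. The one analysis it calls a sensitivity analysis concerns severity: "sensitivity analyses were performed by examining the outcomes separately for those with mild versus moderate audiometric hearing loss".

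The Sample Size and Statistical Power paragraph gives the counts. Enrolment resulted in "172, 171 and 180 adults with mild or moderate audiometric hearing loss assigned to the AB, CD, and EF groups". It continues: "Of these, 152, 133, and 138 completed all three sessions for groups AB, CD, and EF, respectively". It notes that attrition was below expectation but does not compare the arms. Benefit is defined at both six weeks (S1 minus S2) and six months (S1 minus S3), and neither is named as the single primary time point.

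The protocol shows how scores come to be missing. Section 20.4 makes the questionnaire fields mandatory, so a missing PHAP or HHIE score reflects a missed session or an exit, not a skipped item. At Session 2 the aided questionnaires (Section 13.5.1: "The participant will complete these questionnaires on REDCap without assistance") come before the participant is asked about keeping the aids. For someone who will not keep them, Section 13.5.3 says "Complete Exit form in REDCap following instructions", and Section 13.5.4 adds: "If participant is returning the hearing aids, a refund needs to be processed". For the same situation Section 15.0 says "Fill out exit questionnaire if participant still wants to withdraw".

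**The concern.** Multivariate-normal MCMC imputation with no delta or pattern adjustment is a missing-at-random method. Given the variables in the model, people who left are assumed to have benefited as much as similar people who stayed. One documented route out is handing the aids back for a refund, which plausibly goes with poor benefit. Other non-completers kept the aids or did not attend, and returns by arm are not reported.

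If leavers did worse than imputed, each arm's mean is overstated in proportion to its dropout. CD and EF have about twice the dropout of AB, so the contrast shifts towards no difference, which is the conclusion the trial seeks. The severity split uses the same assumption. The per-protocol analysis is undefined, and if it means completers it leaves out the same people. A conclusion that depended on the imputation would not be visible to a reader.

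Sections 13.5.3 and 15.0 also differ on whether returning the aids by itself ends participation. This decides which returners have Session 3 scores.

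**Working it through.** **Inputs.** From the SAP: assigned 172, 171, 180; completed 152, 133, 138; margins 5.5 (PHAB global) and 6.5 (HHIE total benefit); SDs 11 and 13; one-sided 0.025 per comparison; AB effect versus placebo 11 PHAB points. Assumed, because the documents give no value: D, the amount by which non-completers' true benefit lies below that of completers in the same arm.

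**The plan's own figure.** With margin 5.5, SD 11, true difference 0 and one-sided 0.025, the noncentral t gives 80.1% power at 64 per group and 79.5% at 63. The stated 64 reproduces, and HHIE gives the same.

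**Non-completion.**
- AB: 20/172 = 11.6%
- CD: 38/171 = 22.2%; ratio to AB 1.91 (95% CI 1.16 to 3.15), Fisher p = 0.010
- EF: 42/180 = 23.3%; ratio to AB 2.01 (1.23 to 3.27), Fisher p = 0.005

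**Bias and error, Session 2 scores not used.** Let a be an arm's non-completion rate. Imputing at the completers' level overstates that arm's mean by a × D, so the bias in the contrast is (a_test − a_AB) × D = 0.106 × D (CD) or 0.117 × D (EF). The standard error is 11 × √(1/152 + 1/133) = 1.306 (CD) and 11 × √(1/152 + 1/138) = 1.293 (EF). The chance of declaring non-inferiority when the true difference is exactly -5.5 is Φ(bias/SE − 1.96).

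| D | Bias CD | Error CD | Bias EF | Error EF |
|---|---|---|---|---|
| 0 | 0 | 2.5% | 0 | 2.5% |
| 5.5 | 0.58 | 6.5% | 0.64 | 7.2% |
| 11 | 1.17 | 14% | 1.29 | 17% |

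At D = 11 the bias is 21% (CD) and 23% (EF) of the margin. HHIE, with D scaled to SD 13, gives the same fractions and error rates. The bias cancels if the deficit in AB non-completers is 1.91 (CD) or 2.01 (EF) times that in the test arm.

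**With Session 2 scores in the imputation.** Simulation: 2,000 trials per cell, true contrast -5.5, S2 and S3 benefit bivariate normal with SD 11, deficit D at both sessions, imputation within arm, 20 imputations, Rubin pooling, S2–S3 correlation 0.5 to 0.7 (assumed). With D = 0 the error is 1.9–2.9%.

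| Case | CD | EF |
|---|---|---|
| D = 11, half of non-completers have S2 | 6.7–8.1% | 8.3–9.7% |
| D = 11, all have S2 | 3.9–6.6% | 4.1–7.8% |
| D = 5.5, half have S2 | 4.2–4.5% | 4.6–5.0% |

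**Zero benefit for those who return the aids.** Let B be AB completers' mean benefit, which the documents do not give. If half of non-completers returned the aids and had zero benefit, there is no inflation at B = 11. At B = 20 the error is 5.8% (CD) and 6.7% (EF).

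**Tipping point.** Lower the imputed values by delta in the test arm's non-completers only. Non-inferiority is lost at delta = (margin + observed difference − 1.96 × SE) / a_test.

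| Observed PHAB difference | CD | EF |
|---|---|---|
| 0 | (5.5 − 2.56)/0.222 = 13.2 | (5.5 − 2.54)/0.233 = 12.7 |
| -1 | 8.7 | 8.4 |
| -2 | 4.2 | 4.1 |

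For HHIE at -2 the values are 6.6 (CD) and 6.4 (EF).

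**Why arm must be in the imputation model.** Take both test arms truly at -5.5, D = 0 and no Session 2 scores. The pooled completer mean relative to AB is -5.5 × (133 + 138)/423 = -3.52. Imputing everyone at that level gives a bias of (5.5 − 3.52) × 0.222 + 3.52 × 0.116 = 0.85 points for CD, and 0.87 for EF by the same steps.

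**The case against.** The strongest reply concerns size. D = 11 is a full SD and the whole AB-versus-placebo effect, applied to every non-completer. If AB completers' benefit were also 11, then at the margin CD and EF non-completers would have to be about 4 points worse than unaided; they reach zero or better only if B is about 15 or more. The intuitive mechanism, people giving up the aids and gaining nothing, produces no inflation at B = 11 even if all non-completers are set to zero (error 2.2% for CD and 2.5% for EF). It does so only at larger B: 5.5% and 6.9% at B = 15, 14% and 19% at B = 20. Under the SAP's planning assumption of no true difference, overturning the result would take a delta larger than the full AB effect.

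This stands as a limit on magnitude. The 14% and 17% are an upper end, and the direction of bias is plausible, not shown.

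It also stands that six-week missingness is no higher than these rates, because Session 2 returners give aided scores before leaving, so the six-month outcome is the exposed one. Missing at random is inferred from the method, not stated. Data logging and other Session 2 measures, if they were in the model, would make it more credible. The difference between Sections 13.5.3 and 15.0 may be only loose wording. The SAP is written in the past tense with final counts, so any added analysis would be post hoc and supportive.

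None of this supplies an analysis that varies the assumption. Whether the observed difference is near 0 or near -2 is not in the documents, and that is what decides whether the result is fragile.

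**Conclusion.** The concern holds and should be fixed. Non-completion is about twice as high in CD and EF as in AB, the imputation as described has no departure from missing at random, and the one listed sensitivity analysis leaves that assumption alone. Under an equal deficit D in all arms, with no Session 2 information, the bias towards non-inferiority is 0.58 to 1.17 PHAB points (CD) and 0.64 to 1.29 (EF) for D from 5.5 to 11. With D = 11 and Session 2 scores in the model for half or all of the non-completers, the error at the margin falls to roughly 4–10%. The deficit, the S2–S3 correlation and the completers' benefit are all assumptions. A result well inside the margin would probably survive; one near it could be reversed without the reader knowing. Confidence is high on the omission and lower on the direction and size of any bias.

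**What to change.** Keep the present imputation as the main ITT analysis, and state that it assumes missing at random. List its variables, impute within arm and include Session 2 scores. Then add, labelled as supportive:

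1. A delta-adjusted tipping-point analysis on CD and EF non-completers, reporting the delta at which the confidence limit crosses 5.5 (PHAB) or 6.5 (HHIE). This is the essential addition, chiefly for the six-month outcome.
2. A scenario that sets benefit at the missed session to zero where the Exit form or refund record documents a return.
3. Return rates and withdrawal reasons by arm and session.

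Report the non-inferiority conclusion together with its robustness to these, without making it conditional on the zero-benefit scenario. Define the per-protocol set. Sections 13.5.3 and 15.0 must be reconciled on whether return of the aids ends participation.

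The cost is SAP wording and, by estimate, a few hours of analysis for item 1, with no new data collection. Items 2 and 3 depend on what the Exit form and the payment-device refund log record; the documents do not show the Exit form's fields, so this needs checking. There is no loss of power, because the main test is unchanged. The downside is a possibly less favourable statement of robustness.

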boundary between clinically significant inferior and non-inferior outcomes. The most widely adopted convention is to set the margin to ½ the effect of the standard of care (Audiology based – AB) relative to placebo, or ½ the pooled standard deviation (D'Agostino et al., 2003; Norman et al., 2003). Following the latter convention, a non-inferiority margin of 5.5 was established for the PHAB global. It also translated, in the pertinent region of the PHAP rating scale, to a change of about ½ scale unit on the 7-point PHAP response scale, which would likely be considered a minimally clinically important change from unaided to aided performance. For the secondary outcome measure, HHIE-total benefit, the treatment effect for AB service delivery relative to placebo was 13 with a common standard deviation of 13 as well ([name] et al., 2017), consistent with observations in several prior studies using the HHIE (Chisolm et al., 2007). Accordingly, following the same rationale described for the PHAB-global, the non-inferiority margin for the HHIE-total benefit score was set to 6.5.

nQuery Advisor (V8.3.1) was used to estimate the sample size needed for the non-inferiority analyses of the comparative effectiveness of fitting methods. Two separate one-sided significance tests of group differences, AB vs Consumer Decides (CD) and AB vs Easy Fitting (EF), were planned for the outcome measures. As a result, the significance level was set to 0.025 (0.05/2). Power calculations estimated that when the sample size in each group was 64, a two group one-sided 0.025 significance level t-test for multiple (two) comparisons will have 80% power to reject the null hypothesis that the test (CD or EF) and standard (AB) are not non-inferior [the difference in means,  $\mu$ CD- $\mu$ AB or  $\mu$ EF- $\mu$ AB, is 5.5 (PHAB), or is 6.5 (HHIE benefit), or farther from zero in the same direction] in favor of the alternative hypothesis. The alternative hypothesis is that the means of the two groups are non-inferior, assuming the expected difference in means is 0 and the common standard deviation is 11 and 13 for the PHAB global and HHIE total benefit measures, respectively. Thus, with three groups and a required N of 64 per group, a total of 192 participants were needed.

3

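### The SAP gives no step that carries between-imputation variance from its 20 imputations into the BCa bootstrap limits; unless results were pooled, non-inferiority limits from imputed data would be too narrow.

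*SAP*

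**What the plan says.** The Analyses paragraph of the SAP is the only account of how the outcomes are analysed. Its steps are:

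- SAS is used to "impute missing data using the Markov Chain Monte Carlo (MCMC) method (n=20 imputations) and the multivariate-normal approach".
- The next stage is introduced with "After addressing the missing data, initial analysis of the effects of fitting method".
- All analyses are then attributed to SPSS, and the inference is "boot-strapped (n=1000; Biascorrected and accelerated, BCa) General Linear Model analyses, t-tests, means, and 95% confidence intervals".
- Both intention-to-treat (ITT) and per-protocol (PP) analyses are reported. PP is not defined.

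The decision rule is in Sample Size and Statistical Power: "Two separate one-sided significance tests of group differences, AB vs Consumer Decides (CD) and AB vs Easy Fitting (EF), were planned for the outcome measures", each at one-sided 0.025. For the primary outcome "a non-inferiority margin of 5.5 was established for the PHAB global"; for HHIE-total benefit the margin is 6.5. On completion, after giving 172, 171 and 180 participants with mild or moderate loss assigned to AB, CD and EF, the SAP says: "Of these, 152, 133, and 138 completed all three sessions for groups AB, CD, and EF, respectively".

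Neither document mentions pooling, Rubin's rules or between-imputation variance, or says whether the bootstrap was run within each imputed set, on one set or on a combined file.

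**The concern.** Multiple imputation gives valid limits only if the final standard error has two parts: the average variance within a completed data set, and the variance of the estimate between data sets. The second part is the price of not having seen the missing values. A BCa interval is a pair of adjusted percentiles from resampling the rows of one data set. Applied to a completed set, it contains the first part only. Read literally, the SAP ends with that kind of interval.

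In this trial the error would run in the unsafe direction. Non-inferiority is declared when a confidence limit clears the margin, so a limit that is too narrow makes it easier to declare CD or EF non-inferior. Non-completion is also about twice as high in the two arms under test as in the reference arm.

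**Working it through.** **Inputs from the SAP.** One-sided alpha 0.05/2 = 0.025; SD 11 and margin 5.5 (PHAB global); SD 13 and margin 6.5 (HHIE-total benefit); assigned n = 172 AB, 171 CD, 180 EF; completers c = 152, 133, 138.

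**Assumed, because the documents do not give it.** R², the share of outcome variance that the imputation model explains, varied from 0 to 0.7. Data are taken as missing completely at random, which isolates the variance question.

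**1. The plan's own figure.** The SAP's power statement reads: "when the sample size in each group was 64, a two group one-sided 0.025 significance level t-test for multiple (two) comparisons will have 80% power". With SD 11, margin 5.5 and true difference 0, the exact noncentral t gives 79.5% power at 63 per group and 80.1% at 64. The figure reproduces; sample size and alpha are not in question.

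**2. Missing fractions.** AB 20/172 = 11.6%; CD 38/171 = 22.2%; EF 42/180 = 23.3%. These count failure to complete all three sessions, so they are an upper bound for the 6-week outcome.

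**3. Variances of the arm difference.** Sums run over AB and the self-fit arm.
- Within a completed set: W = SD² Σ(1/n)
- Correct variance, many imputations: V = SD² Σ[R²/n + (1 − R²)/c]
- Apparent variance when the 20 values per person are averaged: A = SD² Σ[c/n + (1 − c/n)R²]/n
- True variance of an estimate from one completed set: S = V + (V − W)

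**4. EF against AB, R² = 0.**
- W = 121(1/172 + 1/180) = 1.376; SE 1.173; half-width 1.96 × 1.173 = 2.30
- V = 121(1/152 + 1/138) = 1.673; SE 1.293; half-width 2.54
- A = 121(152/172² + 138/180²) = 1.137; SE 1.066; half-width 2.09
- S = 1.673 + (1.673 − 1.376) = 1.970; SE 1.404

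One-sided error = 1 − Φ(1.96 × SE used / SE true):
- averaged limits: ratio 1.173/1.293 = 0.907, 9.3% too narrow, error 3.8%
- averaged values: ratio 1.066/1.293 = 0.824, 17.6% too narrow, error 5.3%
- one set: ratio 1.173/1.404 = 0.836, 16.4% too narrow, error 5.1%

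**5. Across R².** The ratios do not depend on SD, so they apply to HHIE as well. Each cell gives percent too narrow, then one-sided error.

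| Route | CD, R² 0 | CD, R² 0.7 | EF, R² 0 | EF, R² 0.7 |
|---|---|---|---|---|
| Averaged limits | 9.0%; 3.7% | 3.0%; 2.9% | 9.3%; 3.8% | 3.1%; 2.9% |
| Averaged values | 17.1%; 5.2% | 5.5%; 3.2% | 17.6%; 5.3% | 5.6%; 3.2% |
| One set | 16.0%; 5.0% | 5.7%; 3.2% | 16.4%; 5.1% | 5.9%; 3.3% |

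**6. Simulation.** With 20 proper normal imputations, the same counts, the true difference at the margin and R² from 0 to 0.7, one-sided error was 2.9–4.1% for averaged limits, 3.1–5.8% for averaged values and 3.2–5.6% for one set. Rubin's rules gave 2.3–2.8%. Combining bootstrap draws across the 20 sets gave 2.4–2.9%.

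**The case against.** The strongest reply is that silence is not evidence. The SAP does not say that between-imputation variance was dropped, and the words introducing the analysis stage only order the steps. If Rubin's rules were applied and not written down, the error is close to 2.5% and nothing is wrong except the reporting. This stands. A reader might infer that the reported limits are too narrow and that the error does exceed 0.025; the documents do not support either as a statement of fact.

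A reader might also infer that BCa bootstrapping and multiple imputation cannot be combined, so that every direct route loses the variance. That is wrong. The spread of the bootstrap draws within each set is a standard error and can be pooled. Combining the draws from all 20 sets also carries both components, as step 6 shows. What remains is narrower: a BCa limit from a completed set does not itself carry both components, and the SAP names no step that adds the second.

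The practical effect may be small. For EF against AB at R² = 0, averaged limits would change the PHAB conclusion only if the observed deficit lay between 5.5 − 2.54 = 2.96 and 5.5 − 2.30 = 3.20. With averaged values the upper end becomes 5.5 − 2.09 = 3.41. Power at a true difference of 0, with correct pooling, stays about 99%. This also stands, for the full-sample comparisons. Finally, the simulations behind these ranges used normal data, and the first set used t-intervals in place of BCa. That should matter little for the size of the missing variance component, but the figures are approximate.

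**Conclusion.** The concern holds in conditional form. The SAP generates 20 imputations and then names an inference method that, applied to completed data, leaves out between-imputation variance, with no stated step to restore it. If the limits came from averaged limits, averaged values or a single set, those compared with 5.5 and 6.5 would be about 3 to 18% too narrow, and the one-sided error per comparison about 2.9 to 5.8% instead of 2.5%.

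The size rests on an assumed R² of 0 to 0.7, on data missing completely at random, and on Session 3 non-completion as the missing fraction. Bias from informative withdrawal is a separate matter and is not addressed here.

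The scope is analyses that use imputed data, chiefly ITT. A PP analysis restricted to completers would be unaffected, but the SAP does not say that PP means this. The separate mild and moderate analyses have less room: at 64 per group with complete data the PHAB half-width is already 1.96 × 11 × √(2/64) = 3.8 against the margin of 5.5.

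**What to change.** State in the SAP how the 20 imputed data sets are combined, and define the PP set. For every analysis on imputed data, replace the BCa limits with a limit that carries both variance components:

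- In each of the 20 sets, estimate the arm difference (CD − AB, EF − AB) and its model or bootstrap standard error. Pool by Rubin's rules with small-sample degrees of freedom, and compare the pooled 95% limit with 5.5 or 6.5.
- Two alternatives are acceptable: take limits from the bootstrap draws combined across all 20 sets, or resample the incomplete data and impute within each resample.

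If pooling was already done in one of these ways, the cost is a sentence. If not, it is a rerun on existing data with no new collection. The ITT half-widths would then widen somewhat; for averaged limits in EF against AB at R² = 0, from 2.30 to 2.54 on PHAB global.
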